TRuST	Tayside Randomisation System
TMF	Trial Master File
TMG	Trial Management Group
TSC	Trial Steering Committee
UoD	University of Dundee
WOCBP	Women of childbearing potential

II. TRIAL SUMMARY

Trial Title	A randomised, open-label, multifactorial, multicentre, platform trial using a range of repurposed anti-inflammatory treatment to improve outcomes in patients with bronchiectasis within the EMBARC clinical research network.	
Short title	AIR-NET- Testing anti-inflammatories for the treatment of bronchiectasis	
Clinical Phase	II	
Trial Design	Randomised, open-label, multifactorial, multicentre, platform trial	
Trial Participants	Bronchiectasis patients with active neutrophilic inflammation	
Planned Sample Size	Sample size for each arm is given below.	
Treatment duration	28 days	
Follow up duration	56 days	
	Objectives	Outcome Measures
Primary	To evaluate the effect of a range of interventions compared to usual care on the activity of Neutrophil elastase in sputum	Sputum neutrophil elastase activity at day 28
Control arm	Arm 1: Usual care Participants will be contemporaneously randomised to the control arm until trial end	
Open treatment arms	Arm 2: n=42, disulfiram - two 200mg oral tablets once daily Arm 3: n=42, dipyridamole – one 200mg oral prolonged/modified release capsule twice daily Arm 4: n=42, doxycycline – one 100mg oral capsule once daily Additional treatment arms will be added as identified	
Closed treatment arms	Nil, initial trial protocol, no treatment arms have been closed.	
Sub-study		
Trial Participants	Participants recruited to the main trial at the Tayside site will be enrolled in the sub-study	
	Objectives	Outcome measures
Exploratory	To evaluate the effect of a range of interventions compared to usual care on the cardiovascular system	Pulse wave velocity Full-field Laser Perfusion Imaging

III. FUNDING AND SUPPORT IN KIND

FUNDER(S)	FINANCIAL AND NON FINANCIAL SUPPORT GIVEN
LifeArc	Funding

IV. ROLE OF TRIAL SPONSOR AND FUNDER

The roles and responsibilities of the Sponsor and Funder will be detailed in the Clinical Research Agreement.

V. ROLES AND RESPONSIBILITIES OF TRIAL MANAGEMENT COMMITTEES/GROUPS & INDIVIDUALS

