Participants will be randomized to one of the open treatment arms they have been deemed eligible for, or usual care. Treatment will be administered for 28 days, a period which should be sufficient to demonstrate robust anti-inflammatory effects based on previous studies ([name] et al. 2020). All compounds are not currently used in the treatment of bronchiectasis as long-term therapies but have in vitro or in vivo evidence that they target neutrophilic inflammation and are widely available generic drugs which could be rapidly repurposed if shown to be effective. Any repurposed compounds demonstrating an efficacy signal against usual care will then be considered for further large-scale trials. Compounds that do not demonstrate sufficient efficacy or have safety issues will not be studied further ([name] et al. 2020). The Trial Steering Committee will evaluate the trial data to determine which compounds should be prioritised for further trials, and will review applications/proposals to add new experimental arms to the trial.

A sub-study will also be included as an option for those participants enrolled in Tayside. Neutrophilic inflammation is implicated in increased cardiovascular risk in patients with bronchiectasis and our sub-study will constitute a pilot study to determine if the interventions have an effect on biomarkers of cardiovascular risk.

Rationale for open trial treatments:

Arm 2: Disulfiram

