3. OBJECTIVES AND OUTCOME MEASURES/ENDPOINTS

3.1. Table of endpoints/outcomes

Primary Objective		
Objective	Outcome Measures	Timepoint(s)
To evaluate the effect of a range of interventions compared to usual care on the activity of NE in sputum	Activity of sputum NE	Day 0 and 28
Secondary Objectives		
Objective	Outcome Measures	Timepoint(s)
To evaluate the effect of a range of interventions compared to usual care on the activity of NE in sputum	Activity of sputum NE	Days 0, 7, 14 and 56
To evaluate the effect of a range of interventions compared to usual care on time to onset of first bronchiectasis exacerbation	Time to first pulmonary exacerbation (EMBARC definition)	Days 0 to 28
To evaluate the effect of a range of interventions compared to usual care on quality of life	Quality of life-bronchiectasis (QOL-B) respiratory symptom scale, Bronchiectasis Impact Measure (BIM) questionnaire	Days 0, 7, 14, 28 and 56
To evaluate the effect of a range of interventions compared to usual care on clinical benefits	Bronchiectasis exacerbation and symptom tool (BEST) diary	Days 0 to 28
To evaluate the effect of a range of interventions compared to usual care on walking distance	Distance covered during 6-minute walk	Day 0, 28
To evaluate the safety of a range of interventions compared with usual care	Frequency of adverse events (AEs) and serious adverse events (SAEs)	Days 0 to 56
To evaluate the effect of a range of interventions on peripheral blood neutrophil function	Phagocytosis of bacteria Reactive oxygen species generation Degranulation Ex-vivo formation of neutrophil extracellular traps Mass cytometry (endpoints may vary depending on the experimental arm)	Day 0 to 28
Tertiary Objectives		
Objective	Outcome Measures	Timepoint(s)

To evaluate the effect of a range of interventions compared to usual care on bronchiectasis exacerbations	Frequency of pulmonary exacerbations (EMBARC definition)	Days 0 to 28; Days 0 to 56
To develop and validate additional biomarkers in sputum that are linked with clinical outcomes of bronchiectasis	Measure the concentration of MMPs and NETs in sputum, as well as other biomarkers e.g proteomics, bacterial load, microbiome	Days 0, 7, 14,28 and 56
To develop and validate additional biomarkers in blood that are linked with clinical outcomes of bronchiectasis	Measure serum biomarkers of inflammation and redox status	Days 0, 7, 14, 28 and 56

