10. STATISTICS AND DATA ANALYSIS

10.1. Sample size calculation

Given the nature of the trial, there is no overall sample size target, but the numbers of participants required for each treatment arm are:

	Treatment	n	Open/closed to recruitment
Arm 1	Usual care	Randomisation will continue to end of trial	Open
Arm 2	Disulfiram	42	Open
Arm 3	Dipyridamole	42	Open
Arm 4	Doxycycline	42	Open

Sample size calculations have been performed using the “Superpower” package in R version 4.2.1 and verified using simulations.

The primary endpoint is sputum NE at day 28. The standard deviation of log₁₀-transformed NE is estimated to be 0.5, using unpublished data from the ORBIT4 trial. A “moderate” standardised difference (Cohen, 1988) of 0.5 between the control and each treatment arm is targeted, which equates to a log₁₀-difference of 0.25, i.e. a reduction in NE of approximately 44% vs control after 28 days of active treatment. The DPP1 inhibitor Brensocatib achieved >90% reduction in NE, so the targeted difference is realistic.

Aiming to recruit the number of participants per treatment arm as above (to allow for up to 10% dropout), with concurrent equal randomisation to the shared control arm, the trial would have >80% power to detect such a difference at the 1-sided 10% significance level. This assumes adjustment for up to 4 covariates in the ANCOVA model, with a modest R² value of approx. 0.1. In reality, the R² value should be larger than this (based on ORBIT-4), so power should be closer to 90% (see Table 10.1.1) (Haworth et al. 2019).

Table 10.1.1. Power, given R² value of covariates, to detect a standardised difference in log₁₀-transformed NE at day 28 of 0.5 between each treatment arm and the shared control at the 1-sided 10% significance level.

R ² value of covariates (with up to 4 covariates)	Power
0.1	81.8%
0.2	85.1%
0.3	88.5%
0.4	91.9%

The design uses the rationale of randomised phase II screening designs in oncology (Rubinstein et al. 2005). By setting the type I error rate to 10% (higher than the conventional 5% for phase III trials but widely accepted in phase II) and targeting a moderate treatment effect size, the required sample size is restricted while maintaining good power. This allows us to quickly and efficiently evaluate multiple treatment options, screening out those that appear suboptimal, and taking forward any showing a sufficiently promising efficacy signal for confirmation in a larger randomised trial.

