10.3. Statistical analysis plan

The primary analysis will be performed on an intention-to-treat basis. Analysis of covariance (ANCOVA) will be used to compare the log₁₀-transformed NE between the control and each treatment arm after 28 days, with baseline log₁₀-transformed NE included as a covariate in addition to terms for trial arm, minimisation factors and relevant baseline prognostic variables. Missing data will be dealt with using multiple imputation, assuming missing-at-random is an appropriate assumption; methods exploring other mechanisms may be performed as appropriate. The estimated difference between the arms in log₁₀-transformed NE will be presented along with the corresponding 80% confidence interval and 1-sided p-value. Analysis makes a working independence assumption. To account for the re-randomisation of patients, cluster-robust standard errors will be computed (Kahan et al. 2021)

NE over the entire study period will be compared between arms using linear mixed effects models, including fixed effect terms for trial arm, stratification factors and relevant baseline prognostic variables, and a random intercept participant effect. Quality of life outcomes will be compared between arms using a similar approach.

Analysis of time to first exacerbation will be conducted using a Cox regression model incorporating trial arm, stratification factors and relevant baseline prognostic variables. The hazard ratio, 80% CI and 1-sided p-value associated with study arm will be obtained from this model, using cluster-robust standard errors. A Kaplan-Meier plot will be used to illustrate the relative time to first exacerbation in each arm and contemporaneous controls, with proportion of patients exacerbation-free after 28 and 56 days and associated 80% CIs provided.

Safety will be assessed by tabulating AEs that occurred in at least 10% of the safety population participants in either arm; these will be further broken down by severity. Treatment compliance (including number of expected doses taken/missed, number of dose

reductions (if applicable), reasons for missed doses/dose reductions, etc) will be summarised for each treatment arm.

Full details, including planned sensitivity analyses and the approach for handling missing data, will be provided in a separate Statistical Analysis Plan.

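### The one safety table named in section 10.3 shows an event only from 5 of 42 participants in an arm, which is narrower than the protocol's own outcome of AE and SAE frequency

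*Protocol*

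**What the plan says.** The analysis sentence in section 10.3 reads: "Safety will be assessed by tabulating AEs that occurred in at least 10% of the safety population participants in either arm". These events are then broken down by severity. The only other item near it is a summary of treatment compliance. The section mentions no separate handling of serious events and leaves full details to a statistical analysis plan that is not at hand.

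The table of endpoints in section 3.1 gives the safety outcome as "Frequency of adverse events (AEs) and serious adverse events (SAEs", compared with usual care over days 0 to 56. No frequency threshold is attached.

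The Rationale (section 2) links safety to the decision on each drug: "Compounds that do not demonstrate sufficient efficacy or have safety issues will not be studied further". Section 2.1 adds that this is the first use of these drugs in this population and that unknown risks are possible.

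**The concern.** A frequency cut-off is a normal way to shorten a table of common events. Here it is written as the way in which safety is assessed, in small arms. A 10% rule in an arm of 42 hides any event seen in one to four participants, unless the other arm reaches 10%. That is where low-frequency harms of a repurposed drug in a new population would fall.

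The rule also disagrees with section 3.1. A frequency outcome for AEs and SAEs needs all events to be counted by arm, and a table restricted to events at 10% or more cannot supply it. This is a rule that the protocol states, not a detail left open. An analysis plan that followed the sentence literally would inherit the cut-off. At stake is the by-arm comparison of harms with contemporaneous controls, one of the two grounds on which a drug can be dropped.

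**Working it through.** **Inputs.** The arm size is 42 for each of the three drugs (section 10.1). Each arm is compared with contemporaneous controls "with concurrent equal randomisation to the shared control arm", so about 42 controls per comparison is assumed. The cut-off is 10% of the safety population in either arm (section 10.3). The protocol does not define the safety population. I take all 42 as the main case and 38 as a smaller one, borrowing the efficacy allowance "to allow for up to 10% dropout" (42 × 0.9 = 37.8).

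**Arm size.** Section 10.1 says the trial "would have >80% power to detect such a difference at the 1-sided 10% significance level", for a "standardised difference (Cohen, 1988) of 0.5 between the control and each treatment arm is targeted". I used a noncentral t distribution with:

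- 37 evaluable per arm (37.8 rounded down) and four covariates
- d = 0.5/√(1 − R²)
- error df = 2n − 6 = 68
- noncentrality d × √(n/2) × √(1 − 4/(2n − 3)), the last factor allowing for random covariates

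For R² of 0.1, 0.2, 0.3 and 0.4 this gives 81.8%, 85.1%, 88.5% and 91.9%, as in Table 10.1.1. (Without the last factor, 35 per arm gives the same four figures.) So 42 recruited per arm is a sound basis for what follows. The AE threshold is a chosen rule, so there is no stated figure to reproduce for it.

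**Cut-off in participants.** This is the smallest r with r/n ≥ 0.10.

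- n = 42: 10% is 4.2, so r = 5. A count of 1 to 4 (up to 9.5%) is not shown. For n = 41, r is also 5.
- n = 37 to 40: r = 4. A count of 1 to 3 is not shown.

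**Chance of being shown.** For true rate p, the chance that one arm reaches the cut-off is P(X ≥ r), with X binomial(n, p). The chance that the event occurs but is not shown on that arm's count is P(X ≥ 1) − P(X ≥ r).

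| True rate | Reaches 5/42 | Occurs, below 5/42 | Reaches 4/38 | Occurs, below 4/38 |
|---|---|---|---|---|
| 1% | 0.01% | 34% | 0.06% | 32% |
| 2% | 0.15% | 57% | 0.7% | 53% |
| 5% | 5.7% | 83% | 12% | 74% |
| 7.3% | 19% | 77% | 30% | 64% |
| 10% | 41% | 58% | 54% | 45% |
| 21.2% | 96% | 4% | 97% | 3% |

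Example at 5% and n = 42: P(X ≥ 1) = 1 − 0.95^42 = 0.884 and P(X ≥ 5) = 0.057, so the difference is 0.827.

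**Allowing for the either-arm wording.** If controls have the same 5% rate, the event is shown with probability 1 − (1 − 0.0573)² = 11%.

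**Which listed events this touches.** Section 8.9 gives a frequency class to 14 reactions. Ten are classed below 1 in 10 (four for dipyridamole, six for doxycycline), and four are very common (all dipyridamole). For bleeding, Appendix 1 quotes 77 events among 1654 patients on dipyridamole alone in a large stroke prevention trial. That is 77/1654 = 4.7% if each event is one patient, over a follow-up that the appendix does not give. It is close to the 5% row.

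**An imbalance that the table would omit.** Take 4 of 42 on treatment against 0 of 42 in control. Both counts are below 5, so the row is not shown. The one-sided Fisher p-value is C(42,4)/C(84,4) = (42·41·40·39)/(84·83·82·81) = 0.058. That is inside the one-sided 10% level that the trial accepts for efficacy. No safety test is planned; the figure only gives the scale.

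**The case against.** A reader might infer that safety is assessed only from this table, that serious events and anything below 10% are never tabulated, and that four cases of hepatotoxicity or bleeding against none would be invisible to those who choose the drugs. The documents do not support that.

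- The word only is not in section 10.3, and full details go to a separate analysis plan. SAE tables and an overall AE count are often specified there, so their absence from the protocol is not in itself a fault.
- Section 3.1 commits the trial to SAE frequency.
- All AEs are recorded, and SAEs go to the sponsor within 24 hours (section 9.3). The chief investigator and the Data Monitoring Committee review overall safety data, and standard tables are prepared for the safety update report (section 9.5). The committee also reviews each arm after its tenth participant reaches day 28 (section 10.4). No 10% filter is stated for any of these.
- The Rationale has the Trial Steering Committee evaluate the trial data. It does not tie the decision to this table.
- The cut-off applies to either arm, so a low count is shown when the other arm reaches 10%.
- Some known reactions may well appear: the four very common dipyridamole reactions, and photosensitivity, for which Appendix 1 gives 7.3% to 21.2% (19% to 96% chance of reaching 5 of 42).

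All of this stands as a limit on the point, but it does not remove it. Recording, committee review and safety update reports are monitoring and regulatory processes. They do not specify the by-arm comparison with contemporaneous controls in the trial's analysis. The sentence in 10.3 does specify it, with a rule that does not fit section 3.1.

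**Conclusion.** The point holds as an inconsistency inside the protocol. The one safety analysis that section 10.3 names is narrower than the secondary safety outcome in section 3.1, and the two need to be reconciled. At 42 per arm, events seen in up to four participants in each arm fall out of that table (up to three if the safety set is 37 to 40). A 5% event is shown on one arm's count about 6% of the time, or 12% with 38 in the arm.

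These figures assume that the safety set is close to the number randomised, that there are about 42 contemporaneous controls, and that participants are independent. Whether a given reaction is left out depends on its observed count in both arms, so no named event can be said to be omitted in advance. The point does not show that SAEs or low-frequency events go unrecorded or unreviewed. It is worth correcting because the repair is cheap and safety is a ground for dropping a drug.

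**What to change.** Amend the sentence in section 10.3 so that all AEs and all SAEs are tabulated by treatment arm and its contemporaneous controls, giving participants and events by severity, with no frequency cut-off. Keep the 10% threshold only for a summary table of common events, labelled as such. Define the safety population in the same place, so that the denominator is fixed.

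The cost is a wording change and a few longer output tables. All AEs are already recorded in the electronic case report form, so no new data, visits or participants are needed, and neither the sample size nor the primary analysis changes.

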10.3.1. Statistical analysis plan, sub-study

The results from the sub-study assessments will be combined with results from separate trials, conducted in people with bronchiectasis, not connected with this protocol for analysis. A separate statistical analysis plan will be prepared for the sub-study analysis.

10.4. Interim analysis and criteria for the premature termination of treatment arms or the trial

There will be no interim analyses considering early stopping for efficacy or futility in any treatment arms.

There will be an early review of safety and treatment compliance data by the DMC in each treatment arm. This will take place after the 10th randomised participant to the treatment arm has reached 28 days post-randomisation. Based on this review, the DMC will make recommendations to the TSC as to whether recruitment to the treatment arm should stop, continue as planned, or whether any modifications should be considered (e.g. dosing).

10.5. Economic evaluation

No economic evaluation will be performed.

11. DATA MANAGEMENT

11.1. Data collection tools and source document identification

The PI or delegate will maintain source documents for each participant in the trial, consisting of hospital medical records containing demographic and medical information, laboratory data, electrocardiograms, trial questionnaires and the results of any other tests or assessments. The questionnaires will be completed by the participants and act as source data, the completed form will be filed in the ISF. All trial data relevant to a participant's general medical history will be recorded in the medical record. The medical record will be flagged to state that the participant is participating in the AIR-NET trial.

An eCRF, using Castor Electronic Data Capture (EDC) system, will be provided by TCTU. The trial system will be based on the protocol for the trial. Development and validation of the trial database and quality control will be done according to TCTU procedures. The eCRF will not collect more information than is required to meet the aims of the trial and to ensure the eligibility and safety of the participant.

Participants will also have the option to input daily BEST diary data directly into either the Castor electronic Patient Reported Outcomes - Web version or the Castor Connect App which can be downloaded and installed in the participant's mobile or tablet devices. Electronic Patient Reported Outcomes data collected via Web email and Castor Connect App will automatically be stored and synced to the Castor EDC.

The PI may delegate eCRF data entry but is responsible for completeness, plausibility, and consistency of the eCRF. Delegated trial staff will enter the data required by the protocol into the eCRFs following training in the definitions and methods used in completing the eCRF. Any queries will be resolved by the PI or delegated member of the trial team. On completion of data collection, the PI must certify that the data entered are complete and accurate.

Data verification, cleaning and data extraction will be performed as per TCTU local procedures and detailed in the Data Management Plan.

All electronic data will be stored on secure UoD or cloud-based servers which have restricted access and have disaster recovery systems in place.

11.2. Data handling and record keeping

The database is managed in line with all applicable principles of medical confidentiality and UK law on data protection, namely, the Data Protection Act 2018. The Data Controller will be the UoD and the Data Custodian will be the CI.

Development and validation of the trial database, quality control and data extraction will be managed by TCTU. Details will be documented in the Data Management Plan.

11.3. Access to Data

The CI, PIs and all institutions involved in the trial will permit trial related-monitoring, audits, REC review, and regulatory inspection. In the event of an audit or inspection, the CI and/or PI will allow the Sponsor, representatives of the Sponsor or regulatory authorities direct access to all trial records and source documentation.

Anonymised trial data will be kept under the control of the CI for future research use within the UoD and with other research collaborators (commercial and non-commercial). Access to the data will be as described in section 13.7.

11.4. Archiving

Archiving of trial documents will be in compliance with Sponsor Standard Operating Procedures. Medical records will be maintained in compliance with local NHS policy on retention of medical records. The CI will be responsible for arranging the archiving of the TMF and ensuring that research data is archived in a way that will permit accurate reconstruction of the research. Sites will be responsible for archiving local trial records including the ISF and Pharmacy Site File. Sponsor will be responsible for archiving the Sponsor file.

